Standardized High-Intensity Home Exercise Program: The Peloton platform contains thousands of pre-recorded cycling classes with varying levels of intensities and recommendations. Study staff will select cycling protocols from this pre-recorded list for cyclists entering the study at different levels of fitness (beginners, intermediate, or advanced). Participants will be safely increased in RPMs, heart rate, and overall levels of perceived exertion over subsequent weeks of the study to reach study recommendations. Participants will be will be asked to exercise on the Peloton 3 times per week for 50-60 minutes (40 minutes at their target HRR + 5-10 minute warm-up and cool-down) for 12 months and encouraged to exercise using a relatively high cadence (80-90 rpms). To increase engagement, modules containing different professional Peloton instructors will be utilized. All instances of the modules will be similar in terms of aerobic intensity; however they will vary in type of background music and general personality of the instructor. In addition to the selected CYCLE modules, the patient will have the option to join more than 20 daily "live" sessions or select one of 300+ scenic courses on the Peloton platform. These additional options empower each patient to exercise in a manner best suited for them and will facilitate compliance. Considering the Peloton records, stores, and transmits heart rate, power, speed, estimated distance, time and cadence for every exercise session, regardless of whether the patient is completing a CYCLE module, live class or scenic ride, the specific module they complete is not critical as data are recorded, transmitted and downloaded to the study database regardless. Secure data transmission procedures are detailed in Protection of Human Subjects.

Study staff at each site will make bi-monthly calls to patients to address technology issues or compliance obstacles for those patients not meeting exercise recommendations. During these calls, exercise may be

progressed as deemed appropriate based on physiological signs monitored by the Peloton and patient subjective report (see Protection of Human Subjects for details).

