Usual and Customary Care Group: Participants randomized to the UCC group will be asked to maintain their current exercise habits for 12 months. UCC can entail referrals to physical or occupational therapy or voluntary exercise. Due to the overwhelming evidence that those services are beneficial to individuals with PD, we will not restrict individuals from those programs. Similar to the home exercise group, a member of the study team will call these patients twice per month to inquire about activity levels, medication changes and technology assistance with the activity monitoring device and data.

Alternate Data Capture:

Due to the Covid-19 situation, the Cleveland Clinic and the University of Utah are requesting the ability to conduct virtual visits with participants. The Cleveland Clinic will utilize either FaceTime or Zoom, and the University of Utah will utilize the preferred platforms of their institution.

Inclusion/Exclusion Criteria:

Inclusion Criteria:

- a) Adult with a diagnosis of idiopathic PD by a physician or physician extender
- b) Hoehn and Yahr stage I-III
- c) Demonstrate the ability to safely mount and dismount the Peloton stationary cycle
- d) In-home WiFi (Peloton system requires WiFi to transmit exercise data)*

*2017 report indicates WiFi rates of 76% and 83% in Ohio and Utah households respectively

Exclusion Criteria:

- a) Participation in pharmaceutical or behavioral disease modifying PD-related clinical trial or study
- b) Diagnosis of dementia or any neurocognitive impairment that compromises one's ability to provide informed consent.
- c) Implanted deep brain stimulation electrodes
- d) Recommendation for medical clearance using the American College of Sports Medicine (ACSM) Preparticipation Health Screen (Figure 2)³³
 - a. If the ACSM screen recommends medical clearance, the subject must obtain medical clearance by their health care provider prior to participation.
 - b. Those who choose not to obtain physician clearance will not be eligible for participation. Those who do not receive physician clearance for high intensity exercise will not be eligible.
- e) A musculoskeletal issue (arthritis, osteoporosis, back problem) that would limit one's ability to engage in exercise
- f) Neurological disease other than Parkinson's disease (i.e. multiple sclerosis, Huntington's disease)
- g) Current or active cardiac arrhythmia
- h) DeNovo patients (have not begun Parkinson's disease medications).

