- iii. Working memory/set switching: the ratio of time to complete the Trail Making Test B to time to complete the Trail Making Test A.

Descriptive/exploratory motor outcomes are:

- i. Cardiovascular fitness: Six Minute Walk Test distance;
- ii. Postural stability:
 - a. Balance Error Scoring System (BESS) double leg area
 - b. Balance Error Scoring System (BESS) tandem area
 - c. Balance Error Scoring System (BESS) double leg volume
 - d. Balance Error Scoring System (BESS) tandem volume
- iii. Total self-reported falls during the one-year observation period.

Descriptive/exploratory non-motor outcomes are:

- i. Movement Disorder Society Unified Parkinson's Disease Rating Scale Part I: Non-Motor Aspects of
- ii. Experiences of Daily Living (nM-EDL)
- iii. Movement Disorder Society Unified Parkinson's Disease Rating Scale Part II: Motor Aspects of Experiences of Daily Living (M-EDL)

iv. Movement Disorder Society Unified Parkinson's Disease Rating Scale Part IV: Motor Complications. The latter two scales are classified as non-motor rather than motor outcomes because they focus on patient-reported experience of functional and social impacts of the effects of motor symptoms rather than on the symptoms themselves.

Analysis Sets

The inferential and safety analysis set will consist of all randomized patients. The descriptive/exploratory analysis set will consist of all randomized patients who complete baseline procedures for initiating randomized treatment and follow-up, and for whom study follow-up is initiated. Descriptions of baseline variables will use all available data in the inferential and safety analysis set. Inferential and safety outcomes will be analyzed using the inferential and safety analysis set in accordance with the strict intention-to-treat principle, under which all randomized patients are included in analyses in accordance with their randomized treatment assignments, regardless of their post-randomization experience including treatment and dropout from treatment or study. Descriptive/exploratory outcomes will be analyzed using the descriptive/exploratory analysis set.

Missing Data

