In general, these variables will be described and modeled similarly to secondary outcomes, to potentially support future research. Hypothesis testing results, if obtained, will be interpreted descriptively and not to claim benefit or harm on the basis of CYCLE II data. The distributions of patient-reported falls within the course of the study year across patients within each treatment group will be assessed for compatibility with Poisson distribution. If, as is anticipated, overdispersion is observed, then the negative binomial or other models for overdispersed count data will be entertained.

Adverse events

Adverse events will be descriptively tabulated and compared by Common Terminology Criteria for Adverse Events (CTCAE) system/organ class and preferred term. Serious adverse events will be similarly tabulated and described in individual listings including calendar date and interval from randomization, severity grade (1-5), current status, and assessed relatedness to the exercise intervention. Serious adverse events related to the intervention are expected to be few, and formal hypothesis testing will not be performed due to anticipated low statistical power and the multiple testing context.

Effect modification/subgroup analyses

For those outcomes for which a statistically significant effect of the intervention is found, we will examine statistical interactions of the randomized aerobic exercise regimen with study site, age, sex, BMI, employment status, patient-reported intensity of regular pre-study exercise, primary Parkinson's disease symptoms, primary Parkinson's disease symptom, years since Parkinson's disease diagnosis, whether or not the patient reports any falls during the pre-study year, and baseline MDS-UPDRS III value. For potential categorical effect modifiers, we will focus on an overall Wald test rather than p-values for comparisons of specific subgroups. For continuous variables, we will focus on linear interactions. If a linear interaction is detected, however, we will also assess possible nonlinearity in models using restricted cubic spline effects, and we may also choose to reexpress and communicate the effect in terms of categories defined by ranges to better communicate clinical relevance.

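### Adverse events are summarised only by assigned arm over all randomised patients, with no exposure or follow-up time, so any exercise-related excess is diluted by patients who never start, stop or leave

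*SAP*

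**What the plan says.** SAP, Analysis Sets, uses one set for efficacy inference and for safety: "The inferential and safety analysis set will consist of all randomized patients". The grouping rule is explicit: "Inferential and safety outcomes will be analyzed using the inferential and safety analysis set in accordance with the strict intention-to-treat principle", with patients kept in their assigned arm "regardless of their post-randomization experience including treatment and dropout from treatment or study". A narrower set is defined for descriptive and exploratory outcomes, namely "all randomized patients who complete baseline procedures for initiating randomized treatment and follow-up, and for whom study follow-up is initiated". Self-reported falls are among those outcomes, so falls and adverse events are reported on different denominators.

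SAP, Adverse events, says: "Adverse events will be descriptively tabulated and compared by Common Terminology Criteria for Adverse Events (CTCAE) system/organ class and preferred term". It mentions no person-time, no on-exercise period and no subset who started. Serious events are also listed individually with, among other items, time since randomisation, severity grade and relatedness to the intervention. For these, "formal hypothesis testing will not be performed due to anticipated low statistical power and the multiple testing context".

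The protocol section on the home exercise program says that the cycle stores and transmits data from every session and that these reach the study database. The same section describes staff calls about technology problems or "compliance obstacles for those patients not meeting exercise recommendations". For usual care (UCC), the protocol says that a team member "will call these patients twice per month to inquire about activity levels, medication changes and technology assistance" with the activity monitor.

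**The concern.** Keeping everyone in the assigned arm is conservative for efficacy, because non-adherence moves the estimate toward no difference. For harm the same movement is not conservative: the poorer the adherence, the closer the exercise arm looks to usual care. A reader deciding whether to take up home high-intensity cycling wants to know the risk while cycling. The planned table gives the risk of being assigned a cycle, averaged over however much or little cycling took place.

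Patients who leave the study add a second effect. After they leave, no events of any kind are recorded, yet they count as fully observed. This can occur in either arm and distorts the comparison if departure differs between arms.

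The serious-event listing helps only partly. It gives relatedness and timing from randomisation, but not whether the patient was still cycling, and it gives no rate. For non-serious events no relatedness or timing summary is stated. Since the SAP expects related serious events to be few, non-serious events will probably carry much of the safety information.

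**Working it through.** The documents state no adverse event rate, non-start rate, stopping rate or dropout rate, so there is no safety figure to reproduce. What follows is a range under assumptions.

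**Inputs from the documents.** About 250 patients (protocol, Specific Aims), randomised 1:1 (SAP, Overview), so about 125 per arm; 12 months of intended exercise.

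**Assumed inputs.** Three patterns of non-adherence; unexposed time carries the background risk; events accrue in proportion to time; follow-up is complete.

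**Step 1: exposed share f.** f = (1 − never − stop) + stop × (month of stopping / 12).

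- 5% never start, 15% stop at month 6: 0.80 + 0.15 × 6/12 = 0.875, or 109.4 of 125 person-years.
- 10% never start, 25% stop at month 4: 0.65 + 0.25 × 4/12 = 0.733, or 91.7 person-years.
- 15% never start, 30% stop at month 3: 0.55 + 0.30 × 3/12 = 0.625, or 78.1 person-years.

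**Step 2: dilution.** Let p1 be the 12-month risk when exposed and p0 the background risk.

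- Exercise-arm rate by assignment = f × p1 + (1 − f) × p0.
- Observed excess = f × (p1 − p0).
- Understatement of the exercise-arm rate = (1 − f) × (p1 − p0) / p1.

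With p0 = 0 the understatement is simply 1 − f. With p0 = 10% and p1 = 20% it is (1 − f) × 0.5.

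| Exposed share | Understatement, no background risk | Understatement, 10% vs 20% | Exercise-arm rate shown (true 20%) | Excess shown (true 10 points) |
|---|---|---|---|---|
| 0.875 | 12.5% | 6.25% | 18.75% | 8.75 points |
| 0.733 | 26.7% | 13.3% | 17.3% | 7.3 points |
| 0.625 | 37.5% | 18.75% | 16.25% | 6.25 points |

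In 125 exercise patients, the true excess of 12.5 events (125 × 0.10) appears as 10.9, 9.2 and 7.8.

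**Step 3: what the two columns mean.** The no-background column is a ceiling. It fits events that occur only because of cycling. The planned table covers all adverse events, most of which have some background risk, so for those the understatement of the rate is smaller. The between-arm excess shrinks by the factor f in either case.

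**Step 4: call content.** Set side by side, the exercise-arm text covers technology and compliance and can be read as limited to patients below the recommended exercise level. The usual-care text covers activity, medication changes and device help. Neither mentions adverse events. The exercise passage refers to a human-subjects section, and the protocol elsewhere to one on data and safety monitoring; neither is in the supplied text.

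**The case against.** The strongest reply is that comparing harms by assignment is right for a pragmatic trial. It keeps the protection of randomisation and answers the policy question of what happens when patients are offered this program. That stands. A reader might infer that the by-assignment analysis is itself an error; the documents do not support this. What is missing is a supplement.

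A second reply is that the non-adherence inputs are assumed and the largest percentages apply only without background risk. Both are true, which is why a range is shown. If adherence is high the effect is small.

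A third is that an on-exercise rate conditions on behaviour after randomisation and cannot be set against usual care. That also stands and governs how the table should be labelled. A window that closed at the last logged ride would also misplace the events that made the patient stop.

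Three stronger readings are tempting:

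- **The exploratory set separates never-exercisers, and the SAP then ignores them for harm.** It does not. That set applies to both arms and requires completed start-up procedures and follow-up begun, not a cycling session.
- **Exercise patients are called much less often.** The word bi-monthly permits this, but the usual-care section presents its twice-monthly calls as similar to those in the exercise arm, which favours equal frequency.
- **Adverse events are elicited differently by arm.** This is inference from silence. Neither passage says the calls are the route for collecting adverse events, and the sections that would normally say so were not supplied. Falls are captured by diary and medication is reconciled at each examination, for all participants.

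**Conclusion.** The point holds as a gap in the safety reporting, not as an error in the planned table. The SAP states a by-assignment rule for safety and specifies no exposure-based or follow-up-time rate, although the session data needed for an on-exercise summary are already collected. Any exercise-related excess is multiplied by the exposed share.

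Under the assumed shares of 0.875 to 0.625, the exercise-arm rate is understated by 12.5% to 37.5% for events with no background risk, and by about 6% to 19% at 10% background and 20% exposed risk. The actual size cannot be known from the documents. The direction assumes that cycling raises the risk of the event in question; where it lowers the risk, the benefit would be diluted instead.

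The change should be made: it is cheap and removes a feature by which poorer adherence makes the regimen look safer. The call wording is secondary and conditional on the unsupplied sections. Neither the existence nor the direction of any ascertainment bias can be fixed from what is available.

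**What to change.** Keep the by-assignment table and add to SAP, Adverse events:

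1. Event rates in both arms per person-month of actual follow-up. This deals with patients who leave the study, but not with those who stay in follow-up without cycling.
2. A descriptive table for exercise-arm patients with at least one logged session, giving events per person-month from the first logged session to the last plus a window fixed in advance, so that events causing cessation count as on-exercise. Show later events, and events in patients who never started, separately. Label the table non-randomised and not directly comparable with usual care.

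For the calls, reconcile the two protocol sections on stated content and frequency, checking first whether the human-subjects and safety-monitoring sections already describe a common adverse event question. The SAP is dated January 2024; if follow-up has ended, report any difference in elicitation as a limitation.

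The cost is one extra table from session logs already held, plus follow-up-time rates beside the existing one. The reported exercise harm rate may be somewhat higher.

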Title: Pragmatic Cyclical Lower Extremity Exercise Trial for
Parkinson's Disease

NCT#: NCT04000360

Document Date: January 29, 2024

The Cyclical Lower Extremity Exercise for Parkinson Disease II (CYCLE-II) Study
Principle Investigator: [name].
Site Principal Investigator: [name].

Statistical Analysis Plan: Assessment of Treatment Effect
Study Statistician: [name].

Overview

CYCLE-II is a pragmatic two center, blinded examiner, 1:1 randomized clinical trial to assess whether one year of a home Peloton-cycle based aerobic exercise regimen alters Parkinson's disease progression from that of patients receiving usual care and usual physical activity. The trial is conducted at the Cleveland Clinic and the University of Utah, coordinated by the former. The CYCLE-II study design and basic analytic plan have been published (*Phys Ther* 2021 Nov; 101(11):pzab191, PMCID: PMC8632855). Multiple prespecified quantitative outcomes are hierarchically classified as primary inferential, secondary inferential, and descriptive exploratory outcomes, and assessed in randomly ordered on and off Parkinson's medication examinations at baseline, and again off medication at six and 12 months. Parkinson's disease progression is to be assessed in each group by the estimated annual rates of change of off-medication outcome measures, and the treatment groups are to be compared in intention-to-treat analyses of these estimates.

Study Outcomes

The primary outcome is the total score on the Movement Disorder Society Unified Parkinson's Disease Rating Scale Part III: Motor Examination, an assessment of the motor signs of Parkinson's disease by an examiner masked to the participant's treatment group. Secondary inferential motor outcomes are:

- i. Upper extremity dexterity: time to complete a iPad-based modification of the Nine Hole Peg Test;
- ii. Lower extremity functional mobility
 - a. time to complete an iPad-instrumented Time Up and Go Test;
 - b. average turn velocity on an iPad-instrumented Time Up and Go Test;
- iii. Ambulation gait speed
 - a. average "comfortable speed" velocity on the Ten Minute Walk Test;
 - b. average "fast speed" velocity on the Ten Minute Walk Test;

Secondary non-motor outcomes are:

- i. Neural processing speed: number correct on the New Processing Speed Test;
- ii. Episodic visual memory: Number of locations + number of symbols correctly recalled on the New Symbol Modalities Test;

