In inferential analyses we will presume that missing observations, for whatever reason they may be missing, are technically “missing at random,” i.e., that the unobserved data come from the same distributions, conditional on other variables that have been ascertained in CYCLE II, as do the observed data. Under this assumption, we will multiply impute missing data using both baseline variables and outcome data and will include the multiply imputed outcome data in analyses. Specifically, missing data will be multiply imputed by sequential chained equations using fully conditional specification and the following sets of predictors:

- i. baseline sociodemographic and other characteristics: age, sex, race, ethnicity, residential living situation (alone, with family member or friend, with significant other), employment status (full-time, part-time, retired due to Parkinson's disease related disability, otherwise retired), body mass index (BMI), hand dominance;
- ii. baseline exercise habit: current regular exercise (yes/no), regular aerobic, resistance, and flexibility exercise (yes/no to each), regular home, gym, and outdoor exercise (yes/no to each), exercise intensity;
- iii. Parkinson's disease-related factors: years since diagnosis, leva dopamine equivalent dose, primary Parkinson's disease symptom, patient-reported past year fall count (0, 1-2, 3-12, 13+);
- iv. CYCLE-II characteristics: clinical site, randomized group;
- v. concurrently measured primary and secondary (motor and non-motor) outcomes;
- vi. the same outcome at other visits.

Variables will be imputed by forward order in time with the primary outcome last within each time. At least 25 imputations will be obtained, and trace plots for the primary outcomes will be checked for evident departures for convergence, with burn-in iterations increased until stationarity appears to have been achieved.

Baseline description

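### The SAP gives no rule for a patient who cannot complete a timed or walking test, so by default that inability is imputed as missing at random and receives too good a value

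*SAP*

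**What the plan says.** The Missing Data section of the SAP sets one rule for the inferential analyses: "we will presume that missing observations, for whatever reason they may be missing, are technically" missing at random. It explains this as meaning "that the unobserved data come from the same distributions, conditional on other variables that have been ascertained in CYCLE II, as do the observed data". On that basis "missing data will be multiply imputed by sequential chained equations using fully conditional specification and the following sets of predictors". Besides baseline characteristics, the predictors include site and arm, "concurrently measured primary and secondary (motor and non-motor) outcomes" and "the same outcome at other visits". No reason for missingness is treated differently from any other.

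The Study Outcomes section lists eight secondary inferential outcomes. Six need a completed test:

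- peg test time ("time to complete a iPad-based modification of the Nine Hole Peg Test");
- Timed Up and Go time;
- Timed Up and Go turn velocity;
- comfortable gait speed;
- fast gait speed;
- the Trail Making outcome ("the ratio of time to complete the Trail Making Test B to time to complete the Trail Making Test A").

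The other two, processing speed and visual memory, are counts of correct answers. Follow-up testing is off medication. The inferential set is all randomized patients, so every blank has to be filled.

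Neither document states a time limit, a score, a reason code or separate handling for a patient who attends but cannot complete one of these tests.

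**The concern.** Inability to finish a test because of the disease is an observed outcome, and usually a bad one. It differs from a missed visit or a failed data upload, where the patient would have had a value under normal conditions. An imputation model for a completion time can be fitted only to patients who have a time. Applied to someone who could not finish, it returns the value expected of a similar patient who did. The reason for the blank is knowable at the visit, so this goes beyond the general remark that missing at random cannot be tested.

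The affected outcomes carry the Aim 2 hypotheses and part of Aim 3, and the SAP allows Holm-adjusted claims of benefit on each of them. If inability is unequal between arms, the difference in annual rates is biased, in a direction that depends on which arm has more of it. The within-arm rates, which the SAP also reports and tests, are understated wherever new inability appears during follow-up, even if the difference between arms is not affected.

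**Working it through.** The documents give no rate of inability, standard deviation or effect size for these outcomes, so there is no planned figure to reproduce. The check has two parts: whether anything in the plan handles inability, and how large the error could be under stated assumptions.

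**1. Does another section handle it?**

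- *Outcome description and distributional assessment*: the methods for floor and ceiling effects are for bounded integer scores. Times and velocities are not covered.
- *Sensitivity analyses*: complete-case and available-case analyses also leave out the patient's missing value. Alternative imputation models are unspecified and used only when a result is borderline. No worst-rank or other missing-not-at-random analysis is named.

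**2. How does a 12-month error reach the treatment effect?** Visits are at t = 0, 0.5 and 1 year, with linear time. The slope weight is (t - 0.5) / sum of (t - 0.5)², which gives (-0.5, 0, 0.5) / 0.5 = (-1, 0, 1). Generalised least squares under AR(1), with correlation 0.3 or 0.7, gives the same weights. An error in the 12-month value therefore passes in full into the annual rate.

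**3. Formula.** Shift in treatment effect = pC × gC - pE × gE. Here p is the share unable at 12 months in usual care (C) or exercise (E), and g is the gap between the true or assigned value and the imputed one, in cross-sectional SD.

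**4. Gap under predictors of the SAP's kind (large-sample simulation).** All inputs are assumptions: between-visit correlations of 0.7; a true benefit of 0.27 SD/year; the test missing when the true 12-month value is beyond a threshold; and regression imputation on arm, baseline, 6 months and a same-visit score correlated 0.3 or 0.6 with the test.

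| Same-visit correlation | Unable, usual care | Unable, exercise | Gap (SD) | True effect | After imputation | Attenuation |
|---|---|---|---|---|---|---|
| 0.3 | 3% | 1.6% | 1.05 | 0.270 | 0.257 | 4.8% |
| 0.3 | 5% | 2.8% | 1.01 | 0.270 | 0.251 | 7.2% |
| 0.3 | 10% | 6.0% | 0.96 | 0.271 | 0.237 | 12.3% |
| 0.6 | 3% | 1.5% | 0.89 | 0.269 | 0.258 | 4.3% |
| 0.6 | 5% | 2.8% | 0.86 | 0.266 | 0.249 | 6.4% |
| 0.6 | 10% | 6.1% | 0.82 | 0.271 | 0.244 | 10.0% |

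Attenuation is computed from unrounded values. A stronger same-visit predictor narrows the gap but does not close it. As a rough check on the second row, (0.050 - 0.028) × 1.01 = 0.022, against 0.270 - 0.251 = 0.019. The formula is only approximate here because the table's gap is pooled over the arms.

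**5. Other assumed cases.**

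- Equal inability, 4% in each arm, with equal gaps: shift 0.
- 8% vs 4% with a gap of 2 to 3 SD: 0.04 × 2 = 0.08 to 0.04 × 3 = 0.12 SD/year.
- 10% vs 3% with a gap of 3 SD: 0.07 × 3 = 0.21 SD/year.
- Arms reversed, 4% in usual care and 8% in exercise, gap 1 SD: -0.04 × 1 = -0.04, so exercise looks 0.04 SD/year better than it is.

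**6. Scale.** About 250 patients allocated 1:1 gives 125 per arm. At two-sided 5% and 80% power, the detectable difference is (1.960 + 0.842) × √(2/125) = 0.354 SD of the annual change. With an assumed baseline-to-12-month correlation of 0.7, this is 0.354 × √(2 × 0.3) = 0.27 cross-sectional SD, before any Holm adjustment.

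**The case against.** The strongest reply is that the documents never say non-completion is recorded as missing. Caps and non-completion scores often sit in test instructions or case report forms, and the SAP refers to a published design paper that is not part of these documents. This stands. What can be shown is that no rule is stated, and that without one the blanket presumption applies.

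Second, the imputation is conditional. It uses same-visit MDS-UPDRS III and other outcomes, the patient's own earlier results, arm, disease duration, medication dose and past falls. A severely affected patient receives a poor predicted value. This also stands, and it is why the estimated attenuation is modest.

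Third, inability may be rare. The protocol enrols Hoehn and Yahr I-III patients who can safely use the cycle and have no musculoskeletal problem that limits exercise. With 125 per arm, 5% vs 2% is (0.05 - 0.02) × 125 = 3.75, about four patients. This limits the likely size but does not supply a rule.

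Fourth, giving inability the worst possible score is not a neutral repair. It changes the estimand from the annual rate of change. Zero velocities do not fit the Box-Cox and log-link options in the SAP. Capping Trail Making B need not put the ratio at its worst end: with assumed times, 300 s on B and 150 s on A gives 2.0, while 110 s and 40 s gives 2.75, so the non-completer would look better. For the same reason, sizing the problem in seconds on part B would not be on the scale of the endpoint. These points stand and shape the fix below.

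**Conclusion.** The concern holds for the six secondary outcomes that need a completed test. By default, disease-related inability would be imputed from a model that has seen only completers, and no other section of either document corrects this. Under the assumed rates and correlations, a true benefit of 0.27 SD/year is attenuated by about 4-12%. Shifts of 0.08-0.21 SD/year arise only if the gap is set at 2-3 SD and inability is clearly unequal. The bias is zero if rates and gaps are equal across arms, and flatters exercise if inability is commoner there. Confidence is moderate, because the rate is unknown and an external test manual may already settle the scoring.

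A reader might infer more than this, in three ways that the documents do not support:

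- *That the rule turns the worst outcome into a typical one and erases any benefit.* The predictors carry the patient's severity and history, and the calculation shows partial attenuation.
- *That harm would go unseen.* Adverse events and falls are reported separately.
- *That the headline result is compromised.* The primary MDS-UPDRS III is scored by a rater and does not depend on completing a timed test. Secondary claims are made only if the primary is significant.

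**What to change.** In the SAP:

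1. Limit the missing-at-random imputation to missed visits, technical failures and other reasons unrelated to ability. The protocol allows virtual visits, which may add purely logistical gaps, so the distinction matters.
2. Code from the test record whether each blank is due to inability from disease or safety, and tabulate inability by arm and visit for each test.
3. For the timed and velocity outcomes, prespecify a rank-based (worst-rank) analysis in which inability ranks below every observed value. State which quantity is ranked, and run the analysis whether or not the main result is borderline.
4. For Trail Making, rank inability on B, or on both A and B, directly as worst. Do not compute a ratio from capped times.
5. If a test manual already sets a score for non-completion, state it in the SAP.

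Leaving these blanks unimputed is not enough by itself, because a likelihood-based mixed model fitted to the remaining visits also assumes missing at random. The worst-rank analysis and the tabulation are what bring the inability into the results.

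The cost is a small amount of coding and one extra analysis per outcome, and the rank-based result is not on the annual-rate scale. If inability proves rare, the results will hardly change.
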